6.1.3. Laboratory abnormalities

- Analysis set: Safety analysis set.
- Analysis methodology:

Laboratory tests in this study include several panels: hematology, chemistry, serology, coagulation, urinalysis, and pregnancy test.

The frequency and percentage of participants who experienced laboratory test abnormalities will be summarized according to worst toxicity grade (based on NCI CTCAE version 5.0) observed for each laboratory assay. Summaries of laboratory

tests results by visit may be provided. Summaries for change from baseline and percent change from baseline for the laboratory tests may be provided, if deemed necessary. Shift tables may be provided for selected laboratory tests.

The summaries will be presented for the entire on-treatment period and for the various parts of the study (by dose level for Parts 1A and 1B, by arm for Part 2), and will not be presented by treatment cycle.

Hematology, serology, and coagulation lab results can be combined into one summary output. Separate summaries will be created for chemistry tests. Urinalysis and pregnancy tests will not be summarized and will only be listed in data listings. Shift tables may be provided for selected laboratory tests.

- Missing data: Intermediate missing values (ie, values collected between baseline and the last study measurement) will not be imputed.

6.1.4. Vital Sign Abnormalities

Vital signs including temperature, pulse rate, respiratory rate, and blood pressure, will be assessed.

- Analysis set: Safety analysis set.
- Analysis methodology:

The vital signs will be generally considered as continuous endpoints. However the summaries of vital signs as continuous variables will not be provided as they may not be clinically meaningful. Instead, vital signs during the on-treatment period will be summarized by the categories of abnormality as specified in [Appendix 1](#). Shift tables will not be provided unless deemed necessary.

- Missing data: Intermediate missing values (ie, values collected between baseline and the last study measurement) will not be imputed.

6.1.5. Heart rate corrected QT interval

- Analysis set: Safety analysis set.
- Analysis methodology:

Changes from baseline for the ECG parameters QT interval, heart rate, QTcF, PR interval, and QRS complex will be summarized by treatment and time.

The number (%) of participants with maximum postdose QTcF values and maximum increases from baseline in the following categories (Table 2) will be tabulated by treatment:

Table 2. Safety QTcF Assessment

Degree of Prolongation	Mild (ms)	Moderate (ms)	Severe (ms)
Absolute value	>450-480	>480-500	>500
Increase from baseline		30-60	>60

If more than 1 ECG is collected at a nominal time after dose administration (for example, triplicate ECGs, the mean of the replicate measurements will be used to represent a single observation at that time point. If any of the 3 individual ECG tracings has a QTcF value >500 ms, but the mean of the triplicates is not >500 ms, the data from the participant's individual tracing will be described in a safety section of the CSR in order to place the >500 ms value in appropriate clinical context. However, values from individual tracings within triplicate measurements that are >500 ms will not be included in the categorical analysis unless the average from the triplicate measurements is also >500 ms. Changes from baseline will be defined as the change between the postdose QTcF value and the average of the time-matched baseline triplicate values on Day -1, or the average of the predose triplicate values on Day 1.

In addition, an attempt will be made to explore and characterize the relationship between plasma concentration and QT interval length using a PK/pharmacodynamics modeling approach. If a PK/pharmacodynamics relationship is found, the impact of participant factors (covariates) on the relationship will be examined.

The analysis of ECG results will be based on participants in the safety analysis set with baseline and on-treatment ECG data. Baseline ECG is defined as the most recent ECG prior to Cycle 1 Day 1 dosing. ECG measurements (an average of the triplicate measurements) will be used for the statistical analysis and all data presentations. Any data obtained from ECGs repeated for safety reasons after the nominal time-points will not be averaged along with the preceding triplicates. Interval measurements from repeated ECGs will be included in the outlier analysis (categorical analysis) as individual values obtained at unscheduled time points.

QT intervals will be corrected for HR (QTcF) using standard correction factors (ie, Fridericia's (default correction), Bazett's, and possibly a study-specific factor, as appropriate). Data will be summarized and listed for QT interval, HR, RR interval, PR interval, QRS complex, QTcF (and other correction factors, eg, QTcB as

appropriate), and by dose. Individual QT (all evaluated corrections) intervals will be listed by time and dose. The most appropriate correction factor will be selected and used for the following analyses of central tendency and outliers and used for the study conclusions. Descriptive statistics (n , mean, median, standard deviation, minimum, and maximum) will be used to summarize the absolute value of the corrected QT interval and changes from baseline in corrected QT after treatment by dose and time point. Additional analysis may be performed if needed.

- Missing data: Intermediate missing values (ie, values collected between baseline and the last study measurement) will not be imputed.

6.2. Secondary Endpoints for Part 1

6.2.1. Pharmacokinetic Analysis

6.2.1.1. PK Parameter Analysis

- Analysis set: PK Parameter Set
- Analysis methodology:

In Part 1, following single dose administration of PF-07265028, plasma PK parameters including the C_{max} , T_{max} , AUC_{last} , $AUC_{tau,ss}$ and if data permit, AUC_{inf} , CL/F , V_z/F , and $t_{1/2}$ will be estimated. Following multiple doses of PF-07265028, steady-state PK parameters including $C_{max,ss}$, $T_{max,ss}$, $AUC_{last,ss}$, $AUC_{tau,ss}$, $C_{min,ss}$, CL_{ss}/F , and if data permit, V_{ss}/F , $t_{1/2}$, and R_{ac} ($AUC_{tau,ss}/AUC_{tau,ss}$) will be estimated. In Part 2 participants Not in food-effect subset, following multiple doses of PF-07265028, C_{min} will be reported. In participants in food-effect subset, steady-state PK parameters including $C_{max,ss}$, $T_{max,ss}$, $AUC_{last,ss}$, $AUC_{tau,ss}$, $C_{min,ss}$, CL_{ss}/F under fasted and fed conditions will be estimated. In Part 1 and Part 2, following multiple doses of sasanlimab, C_{min} in selected cycles will be reported.

The single-dose and steady-state PK parameters will be summarized descriptively (n , mean, standard deviation, CV, median, minimum, maximum, geometric mean and its associated CV) by dose, cycle, and day.

Trough concentrations (C_{min}) will be plotted for each cohort using a box-and-whisker plot by cycle and day within cycle in order to assess the attainment of steady state. Dose normalized C_{max} , AUC_{last} , AUC_{tau} (at steady state) will be plotted against dose (using a logarithmic scale) by cycle and day. These plots will include individual participant values and the geometric means for each dose. These plots will be used to help understand the relationship between the PK parameters and dose.

For the evaluation of the food effect, PF-07265028 plasma concentration-time data will be compared on days taken under fasted (Reference) and fed conditions (Test). PK parameters ($C_{max,ss}$, $T_{max,ss}$, $AUC_{last,ss}$, $AUC_{tau,ss}$) of PF-07265028 given under fasted and fed conditions will be summarized descriptively. Natural log transformed AUC and C_{max} values will be analyzed using an analysis of variance model and treatment as fixed effects. Estimates of the mean differences (Fed-Fasted) and

corresponding 90% CI will be obtained from the model. The mean differences and 90% CI for the differences will be exponentiated to provide estimates of the ratios of geometric means (Fed/Fasted) and 90% CI for the ratios.

- Missing data: missing parameter data will be handled according to [Section 5.3.4](#).

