2.2.6. Nonclinical Pharmacokinetics and Metabolism

Details of the nonclinical ADME properties of PF-07265028 are provided in the PF-07265028 IB.

The predicted human plasma clearance and volume of distribution of PF-07265028 are 5 mL/min/kg and 5 L/kg respectively, with an effective half-life of 12 hours. High to complete absorption following oral administration is expected, with an estimated oral bioavailability of 56% at the predicted efficacious dose of 140 mg QD.

The major route of clearance for PF-07265028 is predicted to be CYP3A4-mediated oxidative metabolism, with minor contributions from CYP3A5, 2D6, 2J2, and 1A1 ($f_{m, CYP3A} = 0.80$). No human-specific metabolite was observed in hepatocytes or liver microsomes.

Human plasma protein-binding was measured, with a fraction unbound of 0.0674. Human blood-to-plasma ratio was measured, with a ratio of 1.1.

PF-07265028 is a potential perpetrator of DDIs by time-dependent inhibition of CYP2D6, reversible inhibition of CYP3A, UGT1A1, and transporter-mediated inhibition of P-gp, BCRP, and OCT1 at the clinically relevant dose of 140 mg QD. Potentially, UGT1A9 and MATE2K could also be inhibited at higher doses of PF-07265028. In isolated human hepatocytes treated with PF-07265028, no significant induction of CYP1A2 was observed; however, a concentration-dependent downregulation of CYP3A4 and CYP2B6 mRNA and enzyme activity was observed, and the potential for induction of these enzymes in cells could not be determined.

PF-07265028 was highly permeable in RRCK cells, with an apparent permeability of $\sim 9 \times 10^{-6}$ cm/s. PF-07265028 is a substrate of MDR1 (P-gp) and BCRP efflux transporters with low apical-to-basolateral permeability ($P_{app,AB}$) and high ERs in MDCK-MDR1 (NIH) cells ($P_{app,AB}$ of 0.29×10^{-6} cm/s and ER of 110) and MDCK-hBCRP cells ($P_{app,A-B}$ of 1.1×10^{-6} cm/s and ER of 31.9). PF-07265028 is not a substrate of OCT1 in vitro.

Since the absorption in human is predicted to be high, and the predominant clearance mechanism is expected to be via metabolism, the potential risk of DDIs due to transporter inhibition for PF-07265028 as a victim is low.

Based on GastroPlus simulations, the oral absorption of PF-07265028 is not anticipated to be sensitive to stomach pH changes.

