4.1.3. Food Effect Assessment

In Part 1A or Part 2, the effect of food on PF-07265028 PK will be evaluated in at least 6 evaluable participants at a dose level that was tolerated when PF07265028 was administered with empty stomach. The food effect assessment will be performed in Part 1A if treatment-related Grade ≥ 2 GI toxicity is observed in $\geq 30\%$ participants with a minimum of 6 participants enrolled in total across all dose levels. Otherwise, the food effect assessment will be performed in a subset of participants from Part 2. Each participant will serve as their own control in which PK profile during a dose interval will be assessed when drug is administered with under fasted and fed conditions on Cycle 1 Day 15 and Day 16, respectively.

On Cycle 1 Day 15, participants will receive an oral dose of PF-07265028 under the fasted condition (overnight fasting of at least 6 hours; water permitted except for 1 hour before and 1 hour after drug administration). On Cycle 1 Day 16, participants will receive another oral dose of PF-07265028 with a high-fat, high-calorie meal (breakfast) following 6-hour overnight fasting (water permitted except for 1 hour before and 1 hour after drug administration). Serial PK samples will be collected after each dose on Day 15 and Day 16 per the [SoA Table 4](#). Subsequently, participants will receive the remaining study intervention under an empty stomach condition. Participants who have dietary or other restrictions that preclude a 6-hour overnight fast (water permitted) or consumption of the high-fat, high-calorie meal will not be required to participate in this assessment. Details regarding PF-07265028 administration and food requirements for participants in the food-effect assessment are provided in [Section 6.1.1.1](#).

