These empty stomach requirements may be removed (via a letter to the investigators) if results from the food-effect subset indicate there is no clinically meaningful effect of food on the PK of PF-07265028. If food is demonstrated to improve tolerability for participants included in the cohorts where PF-07265028 is administered with food, participants in all cohorts may be instructed to take PF-07265028 with a meal.

Food Requirements for the Food-Effect Subset

Participants enrolled in the food-effect subset will take PF-07265028 under the fasted and fed conditions on Cycle 1 Day 15 and Day 16, respectively, and under empty stomach condition for the remaining portion of the study.

Fasted condition: Following an overnight fast of at least 6 hours, PF-07265028 will be administered and continue fasting for an additional 2 hours postdose. Water will be allowed ad libitum except for 1 hour before and 1 hour after drug administration.

Fed condition: Following an overnight fast of at least 6 hours, participants will start a high-fat/high-calorie breakfast in the clinical sites within 30 minutes prior to and finish breakfast before administration of PF-07265028. No additional food will be allowed until at least 2 hours postdose. Water will be allowed ad libitum except for 1 hour before and 1 hour after drug administration. The breakfast will be high-fat (approximately 50% of total caloric content of the meal) high-calorie (approximately 800-1000 calories with 150, 250, and 500-600 calories from protein, carbohydrate, and fat, respectively) meal.

Food Requirements for Cohorts Evaluating the Effect of Food on PF-07265028 Tolerability

Each dose of PF-07265028 will be administered with a meal and with approximately 8 ounces (240 mL) of water.

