9.3.3.1. Pharmacokinetic Analysis

9.3.3.1.1. Single Dose and Steady State PF-07265028 and Sasanlimab Pharmacokinetic Analysis (with the Exception of Food Effect Assessment)

The plasma concentration time data of PF-07265028 and serum C_{min} for sasanlimab will be summarized by descriptive statistics (n, mean, standard deviation, coefficient of variation, median, minimum, maximum, and geometric mean) according to dosing cohort and time for each part of the study. Exclusions or separate summaries for dose modifications and concomitant medications may be considered in data summaries.

In Part 1, following single dose administration of PF-07265028, plasma PK parameters including the C_{max} , T_{max} , AUC_{last} , AUC_{tau} and if data permit, AUC_{inf} , CL/F , V_z/F , and $t_{1/2}$ will be estimated. Following multiple doses of PF-07265028, steady-state PK parameters including $C_{max,ss}$, $T_{max,ss}$, $AUC_{last,ss}$, $AUC_{tau,ss}$, $C_{min,ss}$, CL_{ss}/F , and if data permit, V_{ss}/F , $t_{1/2}$, and R_{ac} ($AUC_{tau,ss}/AUC_{tau,sd}$) will be estimated. In Part 2 participants Not in food-effect subset, following multiple doses of PF-07265028, C_{min} will be reported. In Part 2 participants in food-effect subset, steady-state PK parameters including $C_{max,ss}$, $T_{max,ss}$, $AUC_{last,ss}$, $AUC_{tau,ss}$, $C_{min,ss}$, CL_{ss}/F under fasted and fed conditions will be estimated. In Part 1 and Part 2, following multiple doses of sasanlimab, C_{min} in selected cycles will be reported.

The single-dose and steady-state PK parameters will be summarized descriptively (n, mean, standard deviation, CV, median, minimum, maximum, geometric mean and its associated CV) by dose, cycle, and day.

Trough concentrations (C_{min}) will be plotted for each cohort using a box-and-whisker plot by cycle and day within cycle in order to assess the attainment of steady state. Dose normalized C_{max} , AUC_{last} , AUC_{tau} (at steady state) and AUC_{inf} (if estimated), and will be plotted against dose (using a logarithmic scale) by cycle and day. These plots will include individual participant values and the geometric means for each dose. These plots will be used to help understand the relationship between the PK parameters and dose.

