4. ANALYSIS SETS (POPULATIONS FOR ANALYSIS)

Data for all participants will be assessed to determine if participants meet the criteria for inclusion in each analysis population.

Table 1. Analysis Sets

Participant Analysis Set	Description
Full Analysis Set (FAS)	All enrolled participants who have been assigned to treatment. Participants are analyzed according to the treatment they were assigned .
Safety Analysis Set (SAS)	All enrolled participants who receive at least 1 dose of study treatment. Unless otherwise specified the safety analysis set will be the default analysis set used for all analyses.

090177e198da3551\Approved\Approved On: 16-Dec-2021 03:17 (GMT)

Table 1. Analysis Sets

Participant Analysis Set	Description
Per-Protocol Analysis Set (DLT-Evaluable Set)	All enrolled participants who had at least 1 dose of study treatment and either experienced DLT or do not have major protocol deviations during the DLT observation period.
mITT Population	All enrolled participants who have received at least 1 dose of study medication; have a baseline assessment and at least 1 post-baseline assessment.
PK Parameter Set	All enrolled participants treated who do not have protocol deviations influencing PK assessment, and have sufficient information to estimate at least 1 of the PK parameters of interest.
PK Concentration Set	All enrolled participants who are treated and have at least 1 analyte concentration above the lower limit of quantitation.
Response Evaluable Set	All enrolled participants who received at least 1 dose of study treatment and had adequate baseline disease assessment. Participants who discontinued early or died will be included.
Pharmacodynamic/ Biomarker Analysis Sets	The Pharmacodynamic/Biomarker analysis population is defined as all enrolled participants with at least 1 of the Pharmacodynamic/Biomarkers evaluated at pre- and/or postdose.
Immunogenicity Analysis Set	The immunogenicity analysis set is a subset of the safety analysis set and includes participants who have at least 1 analyzed sasanlimab ADA/NAb sample.

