5.3.4. Pharmacokinetic Parameters

Actual PK sampling times will be used in the derivation of PK parameters. If a PK parameter cannot be derived from a subject's concentration data, the parameter will be coded as NC (i.e., not calculated). (Note that NC values will not be generated beyond the day that a subject discontinues.)

In summary tables, statistics will not be presented for a particular treatment group if more than 50% of the data are NC. For statistical analyses, PK parameters coded as NC will also be set to missing.

If an individual subject has a known biased estimate of a PK parameter (due for example to dosing error), this will be footnoted in summary tables and will not be included in the calculation of summary statistics or statistical analyses.

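### The food-effect ANOVA names no participant term for a paired comparison, and parameters after one fed dose are labelled as fed steady state

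*SAP*

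**What the plan says.** Protocol 4.1.3 sets up a within-participant comparison in at least 6 evaluable participants: "Each participant will serve as their own control in which PK profile during a dose interval will be assessed" fasted on Cycle 1 Day 15 and fed on Day 16. It does not define *evaluable*. Protocol 6.1.1.1 fixes the order and shows that there is only one fed dose: the two conditions fall on "Day 15 and Day 16, respectively, and under empty stomach condition for the remaining portion of the study".

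For the analysis, SAP 6.2.1.1 and Protocol 9.3.3.1.2 share one sentence: log AUC and Cmax "values will be analyzed using an analysis of variance model and treatment as fixed effects". The fed-minus-fasted difference and its 90% CI are then exponentiated to a ratio of geometric means. SAP 6.5.2 sends Part 2 back to the same text, and no other section supplies a further model term.

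On labels, the SAP has "In participants in food-effect subset, steady-state PK parameters including" Cmax, AUC, Cmin and CLss/F under both fasted and fed conditions. Protocol 9.3.3.1.1 has the same for Part 2 ("In Part 2 participants in food-effect subset, steady-state PK parameters including"), and Protocol 9.3.3.1.2 also uses the steady-state suffix. The food-effect endpoint lists in Protocol 3.1 and 3.2 and SAP 3.2 and 3.5 name Cmax, Tmax and AUC without that suffix, and name no clearance.

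**The concern.** There are two separate faults.

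**Model.** A paired design removes between-participant variance from the comparison only if the model identifies the participant. With treatment as the sole effect, the Day 15 and Day 16 values are treated as two independent groups. The interval then does not have its nominal 90% coverage, and the precision that pairing gives a group as small as 6 is lost.

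**Label.** One fed dose on top of non-fed dosing is not fed steady state. Dose divided by AUCtau equals CL/F only at steady state in the condition studied, so a fed CLss/F from Day 16 does not estimate what its name says. Drug left from earlier doses also enters the Day 16 profile, and the plan does not mention this.

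The ratio and its interval are the only planned inferential summary of the food effect. Protocol 4.1 and 4.2 use the food-effect PK results when considering whether the empty-stomach condition continues, so readers should know what the ratio and its interval measure.

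**Working it through.** The documents give no precision or power figure for this comparison and no derivation of the number 6, so there is no planned figure to reproduce.

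**1. Interval width and coverage**

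Inputs: n = 6 (Protocol 4.1.3) and a two-sided 90% CI (SAP 6.2.1.1). The documents give no CVs. I assume within-participant CV 20-30% and between-participant CV 30-60%, with log-scale variance ln(1 + CV²): vw within, vb between.

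- Half-width as written: t(0.95, 2n−2) × √(2(vb + vw)/n), with t(0.95, 10) = 1.812.
- Half-width paired: t(0.95, n−1) × √(2vw/n), with t(0.95, 5) = 2.015.

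Example, within 25% and between 50%: vw = 0.0606, vb = 0.2231.
- As written: 1.812 × √(2 × 0.2838/6) = 0.557; around a ratio of 1 the interval is 0.57 to 1.75.
- Paired: 2.015 × √(2 × 0.0606/6) = 0.286; the interval is 0.75 to 1.33.
- Width ratio: 0.557/0.286 = 1.95.

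Width as written relative to paired (log scale):

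| Within CV | Between 30% | 40% | 50% | 60% |
|---|---|---|---|---|
| 20% | 1.61 | 1.97 | 2.33 | 2.67 |
| 25% | 1.40 | 1.67 | 1.95 | 2.22 |
| 30% | 1.27 | 1.48 | 1.70 | 1.92 |

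Simulated coverage of the nominal 90% interval as written is 96.8% at 30% within/30% between (correlation 0.50) and 99.9% at 20%/60% (correlation 0.89). The paired interval covers 90% in both cases. By correlation, coverage as written is 89.9% at 0, 91.4% at 0.1, 94.3% at 0.3 and 98.8% at 0.7.

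The widths are equal when 1 − correlation = (1.812/2.015)², that is, at a correlation of about 0.19. Below that the paired interval is slightly wider: at 30% within/10% between, the interval as written is 0.95 times the paired one.

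**2. Point estimate**

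With complete pairs, both models give the same ratio. Complete pairs are not explicitly required. The PK Parameter Set asks only that participants "have sufficient information to estimate at least 1 of the PK parameters of interest", and SAP 5.3.4 adds: "For statistical analyses, PK parameters coded as NC will also be set to missing". As an illustration, take 6 fasted and 5 fed profiles, where the fasted-only participant has twice the typical exposure. The ratio from the model as written is multiplied by 2^(−1/6) = 0.89. A random participant effect would still multiply it by 0.94 (30%/30%) to 0.99 (20%/60%). A fixed participant effect, or restriction to complete pairs, leaves it unchanged.

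**3. Carry-over into Day 16**

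Inputs: once-daily dosing (interval 24 h), and predicted clearance and volume that "are 5 mL/min/kg and 5 L/kg respectively, with an effective half-life of 12 hours" (Protocol 2.2.6). Check: ln2 × 5000/5 = 693 min = 11.6 h, which agrees. I assume linear PK. After 14 earlier daily doses, the Day 15 fasted profile is at steady state for this half-life, so the fasted label is sound.

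- Residual as a fraction of Day 15 AUCtau: f = exp(−ln2 × 24/half-life). At 12 h, f = 0.25 (0.1875 from the Day 15 dose, 0.0625 from earlier doses). At 6, 8 and 16 h it is 0.06, 0.125 and 0.35.
- Observed AUC ratio for a true ratio R: f + (1 − f)R. At f = 0.25, R = 2.0 gives 0.25 + 1.50 = 1.75, R = 1.5 gives 1.38, and R = 0.5 gives 0.63.
- Observed fed/fasted CL/F: 1/1.75 = 0.57 where the true value is 0.50, and 1/0.625 = 1.60 where it is 2.00.
- Cmax, one-compartment model with assumed absorption rate 0.3-2 per h and food changing bioavailability only: 2.0 reads 1.70 to 1.74, and 0.5 reads 0.63 to 0.66.

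**The case against.** The model sentence is ungrammatical, its plural implies a second effect, and the protocol calls each participant their own control. A programmer would probably fit a participant term, and the treatment-only model is the least plausible intention. That stands as a view of intent. But both documents carry the same wording and nothing else supplies the term.

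On the label, the endpoint lists already omit the steady-state suffix, CLss/F is only summarised descriptively, and the modelled quantities are AUC and Cmax. This also stands: the fault is a mismatch between the analysis text and the endpoint lists, and the CLss/F label does not enter the ratio. On carry-over, population PK modelling is allowed (Protocol 9.3.6), and cohorts taking every dose with a meal are possible (Protocol 4.1 and 6.1.1.1). These routes are optional or conditional, so they mitigate the problem without removing it.

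Two stronger readings are tempting. A reader might infer that the wide interval makes the food decision conservative, or that it would cause a real effect to be missed. Neither is supported: the documents set no numeric limit and no rule based on the interval, only a judgement of clinical meaningfulness. A reader might also infer that participants with one profile will be included. That is possible but not stated. *Evaluable* could naturally mean both days, and SAP 5.3.3.2 and 5.3.4 allow affected participants or biased estimates to be excluded.

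**Conclusion.** The point holds in two parts.

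- **Model.** As written, it gives wrong error bars. The interval over-covers for any positive within-participant correlation, and at n = 6 it is wider than the paired interval once the correlation exceeds about 0.19. The factor of 1.3 to 2.7 and the coverage of about 97% to 99.9% rest on assumed CVs. It does not follow that the estimated ratio is biased: with complete pairs it is unchanged.
- **Label.** The fed steady-state labels and fed CLss/F are incorrect as descriptions of one fed dose after non-fed dosing. Under linear superposition the residual drug pulls the ratio toward 1. Its size depends on once-daily dosing, linear PK and a preclinical half-life; the residual is 6% to 35% of Day 15 AUCtau for half-lives of 6 to 16 h. Linearity is uncertain, because Protocol 2.2.6 predicts that the drug is both a substrate and an inhibitor of CYP3A.

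This is a secondary PK analysis. No primary endpoint is affected.

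**What to change.** In Protocol 9.3.3.1.2 and SAP 6.2.1.1:

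1. Analyse ln(AUC) and ln(Cmax) with condition and participant as fixed effects (equivalently, a paired analysis) in participants with evaluable profiles on both Day 15 and Day 16, and define *evaluable* that way.
2. Label the fed values as Day 16 parameters after one fed dose, in line with the endpoint lists, and do not report a fed CLss/F. Make the same change in Protocol 9.3.3.1.1.
3. State, when reporting the ratio, that residual drug pulls it toward 1 and that condition is confounded with day because the order is fixed. Relabelling alone does not remove the attenuation.

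These are wording changes with no new visits, samples or participants. The one statistical cost is small: if between-participant variance is very low (30% within/10% between), the paired interval is about 5% wider at n = 6.
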